1 PROTOCOL SUMMARY

1.1 SYNOPSIS

Protocol title:

A single-arm, 52-weeks, Phase 4 study to assess the efficacy and safety of dupilumab in patients with chronic rhinosinusitis with nasal polyposis (CRSwNP) who are not adequately controlled with existing therapies

Brief title: Dupilumab in Japanese patients with chronic rhinosinusitis with nasal polyp (SINUS-M52)

Rationale:

Dupilumab blockade of interleukin-4 (IL-4) and IL-13 signaling has demonstrated a favorable efficacy and safety profile for the treatment of a variety of atopic disease states, including atopic dermatitis (AD), asthma, and CRSwNP, where type-2 inflammation is a key driver of the underlying disease process. This study will assess the efficacy and safety profile of dupilumab administered as monotherapy to Japanese CRSwNP participants whose disease is not adequately controlled with existing therapies (systemic corticosteroids [SCS] and surgery).

Dupilumab has been approved for the treatment of CRSwNP that is not adequately controlled with existing therapies by the health authority in Japan on the condition that the efficacy and safety of dupilumab monotherapy will be assessed after approval; the efficacy and safety data in the global program were developed with intranasal corticosteroid (INCS) concomitantly administered with dupilumab. Intranasal corticosteroid is not approved for CRSwNP in Japan. Their use for CRSwNP is an off-label use in Japan. The objective of this Phase 4 study is to assess the efficacy and safety of dupilumab as monotherapy (without concomitant INCS) in participants with CRSwNP.

Objectives and endpoints:

Objectives	Endpoints
Primary	

 To assess the efficacy of 24-week treatment with dupilumab 300 mg every 2 weeks (q2w) to reduce nasal polyp score (NPS) in participants with chronic rhinosinusitis with nasal polyposis (CRSwNP) who do not use concomitant intranasal corticosteroid (INCS) 	
 Proportion of participants with NPS improvement from baseline ≥ 1 at Week 24
Secondary	

 To assess the efficacy of 24-week treatment with dupilumab 300 mg q2w on other efficacy endpoints in participants with CRSwNP who do not use concomitant INCS 	
Key secondary efficacy endpoints:
 
 Change from baseline to Week 24 in bilateral NPS Change from baseline to Week 24 in nasal congestion/obstruction (NC) symptom severity score using the CRSwNP nasal symptom diary Change from baseline to Week 24 in opacification of sinuses assessed by computerized tomography (CT) scan using the Lund Mackay (LMK) score 
Other secondary efficacy endpoints:
 
 Change from baseline to Week 24: 
 Total symptom score (TSS), a composite score derived from the nasal symptom diary (includes nasal congestion, loss of sense of smell, anterior and posterior rhinorrhea) Loss of smell symptom severity score using the nasal symptom diary Visual analogue scale for rhinosinusitis Incidence of treatment-emergent adverse events (TEAEs), treatment-emergent serious adverse events (TESAEs), and TEAEs leading to treatment discontinuation

 To evaluate the safety of 24-week treatment with dupilumab in participants with CRSwNP 	
Tertiary/exploratory	

 To assess the efficacy of 52-week treatment with dupilumab under different dosing regimens to participants with CRSwNP who do not use concomitant INCS 	
 Proportion of participants with NPS improvement from baseline ≥ 1 at Week 52 Change from baseline to Week 52 in bilateral NPS Change from baseline to Week 52 in NC symptom severity score using the CRSwNP nasal symptom diary Change from baseline to Week 52 in opacification of sinuses assessed by CT scan using the LMK score Change from baseline to Week 52 in TSS

 To evaluate the safety of 52-week treatment with dupilumab in participants with CRSwNP 	
 Incidence of TEAEs, TESAEs, and TEAEs leading to treatment discontinuation

Abbreviations: CRSwNP: chronic rhinosinusitis with nasal polyposis; CT: computerized tomography; INCS: intranasal corticosteroid; LMK: Lund Mackay; NC: nasal congestion/obstruction; NPS: nasal polyp score; q2w: every 2 weeks; TEAE: treatment-emergent adverse event; TESAE: treatment-emergent serious adverse events, TSS: total symptom score.

Overall design:

This is a Phase 4, open-label, single-arm, multicenter, efficacy and safety study of dupilumab monotherapy in participants with CRSwNP that is not adequately controlled with existing therapies.

This study will investigate the efficacy and safety of dupilumab 300 mg every 2 weeks (q2w) at Week 24, without concomitant administration of INCS.

In addition, in line with Japan label, the study is designed to assess the long-term (52 weeks) efficacy and safety of an initial treatment regimen of dupilumab 300 mg q2w for 24 weeks without INCS, followed by a less frequent dosing regimen (300 mg every 4 weeks [q4w]) up to Week 48 for those participants who demonstrate stable disease* at Week 24. Other participants will receive the q2w regimen up to Week 50.

**Stable disease definition: nasal polyp score (NPS) improvement from baseline to both Weeks 16 and 24 is ≥ 2 points.*

During the study, participants who report deterioration requiring medical or surgical intervention may go to the study site for clinical evaluation. An unscheduled visit may be used for this purpose, and if necessary, the Investigator may consider one of the treatment alternatives described in [Section 6.8.1](#).

Brief summary:

This is a Phase 4, open-label, single-arm, multicenter study to evaluate the efficacy and safety of dupilumab monotherapy in participants aged 18 or older with CRSwNP that is not adequately controlled with existing therapies.

Number of participants:

Approximately 25 participants will be enrolled.

Intervention groups and duration:

Study intervention(s)

- Dupilumab 300 mg q2w
- Dupilumab 300 mg q4w

For participants who have stable disease, the dosing interval can be changed from q2w to q4w at the discretion of the Investigator at Week 24. Participants who change from q2w to q4w will not be permitted to return to the q2w regimen during this study and will receive the q4w regimen until Week 48. Other participants will receive the q2w regimen up to Week 50. The participants will be followed up to Week 52.

Duration of study period (per participant):

- Screening Period (2 to 4 weeks): between Screening Visit (Visit 1) and the first dose of investigational medicinal product (IMP) (Visit 2)
- Intervention Period (up to 52 weeks±3 days)

Investigational medicinal product(s):

- Dupilumab 300 mg

Formulation:

- Dupilumab 300 mg: a 150 mg/mL dupilumab solution in a prefilled syringe to deliver 300 mg in a 2-mL injection

Route of administration: subcutaneous (SC) injection

Dose regimen:

- One injection of 300 mg q2w up to Week 24 (all participants)
- One injection of 300 mg q4w after Week 24 (participants who have stable disease at Week 24)
- One injection of 300 mg q2w after Week 24 (participants who cannot achieve stable disease)

Post-trial access to study medication will not be provided.

Statistical considerations:

[figure not shown]
This postmarketing study is to assess whether dupilumab used without INCS will show similar efficacy to that of dupilumab used with INCS in EFC14280, using the point estimates of the proportion of responders (NPS improvement from baseline ≥ 1) at Week 24. Formal statistical tests for hypotheses (null/alternative) will not be performed.

- **Primary endpoint:**
 - The proportion of responders (NPS improvement from baseline ≥ 1) at Week 24.
- **Key secondary endpoints:**
 - Change from baseline to Week 24 in bilateral NPS
 - Change from baseline to Week 24 in nasal congestion/obstruction (NC) symptom severity score using the CRSwNP nasal symptom diary
 - Change from baseline to Week 24 in opacification of sinuses assessed by computerized tomography (CT) scan using the Lund Mackay (LMK) score

Data Monitoring/Other committee: No

1.2 SCHEMA

Figure 1 - Graphical study design

Abbreviations: D: day; EOS: end of study, EOT: end of treatment; q2w: every 2 weeks; q4w: every 4 weeks; V: visit.

Procedure	D-28 to D-14	Intervention Period							
		W0 D1	W2 D15 (±3 days)	W4 D29 (±3 days)	W8 D57 (±3 days)	W16 D113 (±3 days)	W24 D169 (±3 days)	W40 D281 (±3 days)	W52 D364 (±3 days) EOT/EOS
Visit	V1 (Screening)	V2	V3	V4	V5	V6	V7	V8	V9
CT scan	X ^e						X		X
Nasal Symptom Diary ^f (includes nasal congestion, loss of smell, anterior and posterior rhinorrhea; TSS derived from these 4 items)		←————— daily diary —————→							
VAS for rhinosinusitis		X	X	X	X	X	X	X	X
Vital signs ^g	X	X			X	X	X	X	X
12-Lead ECG (local reading)	X								
AE review		←—————							
SAE review		←—————							
Laboratory assessments (including hematology, biochemistry, and urinalysis) ^h	X	X			X		X		X
Hepatitis B and C; HIV testing; TB testing ⁱ	X					X ^j	X ^j	X ^j	X ^j
Pregnancy test (WOCBP only) ^k	X	X		X	X	X (W12, 16)	X (W20, 24)	X (W28, 32, 36, 40)	X (W44, 48, 52)

Abbreviations: AE: adverse event; CT: computerized tomography; D: day; e-CRF: electronic case report form; ECG: electrocardiogram; EOS: end of study; EOT: end of treatment; HBcAb: hepatitis B core antibody; HBsAb: hepatitis B surface antibody; HBsAg: hepatitis B surface antigen; HCV Ab: hepatitis C virus antibody; HIV: human immunodeficiency virus; IgM: immunoglobulin M; IGAR: Interferon-gamma release assay; IMP: investigational medicinal product; IVRS/IWRS: interactive voice/web response system; MRI: magnetic resonance image; NE: nasal endoscopy; NERD: non-steroid anti-inflammatory drug exacerbated respiratory disease; NP: nasal polyposis; NPS: nasal polyp score; q2w: every 2 weeks; q4w: every 4 weeks; SAE: serious adverse event; SCS: systemic corticosteroids; TB: tuberculosis; TSS: total symptom score; V: visit; VAS: visual analogue scale; W: week; WOCBP: women of childbearing potential.

- a Past medical history, including allergic comorbidities (asthma, aspirin sensitivity, allergic rhinitis, etc.). Surgeries for NP, including number, type and dates of sinonasal surgeries, and polypectomies, in the past will be recorded. Systemic corticosteroid use (number of courses, doses, route of administration, and duration) in the past 2 years before V1 and/or contraindication/intolerance to SCS, as well as long-term antibiotics use (>2 weeks) in the previous year, will be entered in the e-CRF. NERD will be assessed through a specific questionnaire (Appendix 11 [Section 10.11]).
- b Call IVRS/IWRS to register visit and obtain next IMP kit numbers assignment or report potential definitive IMP stop.
- c Investigational medicinal product will be administered q2w (after Week 24, some participants can be administered q4w). Between visits, at site or home administration is allowed after the second dose. Investigational medicinal product will be administered after the completion of all scheduled clinical assessments at the visit or at home. The planned last dose is at Week 48 or 50. For participants who have stable disease at Week 24, the dosing interval can be changed from q2w to q4w at the discretion of the Investigator; the reason for the change in dosing regimen should be recorded in the e-CRF. Other participants will receive the q2w regimen until Week 50. Stable disease is defined as NPS improvement from baseline to both Weeks 16 and 24 of ≥ 2 points.
- d Nasal endoscopy: endoscopy (including use of decongestants before the procedure) will be performed after all other efficacy assessments have been completed for each visit. Standard video sequences will be downloaded by the Investigator to the central reader's secured internet site. For eligibility, central reading of V1 will be used. At V2, the Investigator will review the V1 results from the central reader to confirm entry criteria and reconfirm eligibility based on a review of the inclusion/exclusion criteria and the V2 endoscopy local reading. To confirm eligibility at V2, only the V1 central reading will be made available to the site. In addition, at V2, the Investigator will perform the NE to confirm eligibility score and enter the result in the e-CRF. Thus, the participant will be considered eligible based on a V1 central reading followed by a V2 local reading NPS score of 5 or more and at least 2 on each side.
- e Computerized tomography scan to be done during the Screening Period.
- f Captured daily.
- g Vital signs, including systolic and diastolic blood pressures (mmHg), pulse rate (beats per minute), respiratory rate (breaths per minute), and body temperature (forehead [temporal] temperature; degrees Celsius), and body weight (kg) will be measured at V1 and V2 and subsequent visits prespecified in the SoA. Height (cm) will be measured at V1 only. Vital signs will be measured prior to receiving IMP at the clinic visits in the sitting position, preferably using the same arm at each visit.
- h Hematology: platelet count, red blood cell count, hemoglobin, hematocrit, and total white blood cell count with five-part differential count. Clinical chemistry: blood urea nitrogen, creatinine, glucose (indicate if fasting or nonfasting), uric acid, total cholesterol, total protein, albumin, total bilirubin (in case of values above the normal range, differentiation in conjugated and nonconjugated bilirubin), alanine aminotransferase, aspartate aminotransferase, alkaline phosphatase, lactate dehydrogenase, electrolytes (sodium, potassium, chloride), and creatine phosphokinase. Routine urinalysis: specific gravity, pH, glucose, protein, blood, ketones, urobilinogen, nitrite by dipstick, and microscopic examination (if blood or protein is abnormal).
- i Hepatitis screen: HBsAg, HBsAb, HBcAb or HBcAb IgM and total; HCV Ab. HIV screen: anti-HIV-1 and HIV-2 antibodies. TB blood testing: IGRA. In case of results showing HBsAg (negative) and HBcAb total or HBcAb IgM (positive), HBV DNA testing may be performed prior to enrollment to rule out a false positive if the Investigator believes the participant is a false positive or to clarify the serological status if the Investigator finds it unclear to interpret in the absence of known HBV infection. In case of results showing HCV Ab (positive), HCV RNA testing may be performed to rule out a false positive, if the Investigator believes the participant is a false positive. An IGRA will be performed for diagnosis of both latent and active TB only for participants without a history of active/latent TB.
- j Participant who are HBcAb (positive) and HBV DNA (negative) at Visit 1 will require HBV DNA monitoring at Visits 6, 7, and 8 and the EOT/EOS Visit. If the HBV DNA result becomes positive during the study, the participant will be temporarily discontinued from IMP administration and should be referred to a hepatologist. Investigational medicinal product may be restarted under careful consideration of participant's risks and benefits based on hepatologist evaluation and current treatment guidelines and after consultation with the Medical Monitor.
- k Serum pregnancy test at V1 and urine pregnancy tests q4w thereafter. A negative result must be obtained during the Screening Period before IMP administration. Urinary pregnancy test could be performed at home as part of visit with or without the assistance of a home care provider. In the case of a positive urine pregnancy test, the study intervention will be withheld, and a serum pregnancy test to confirm the pregnancy should be performed as soon as possible. Pregnancy will lead to definitive treatment discontinuation in all cases.

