Participants who have their vaccination moved to before the start of the study can be enrolled into the study only after a gap of 4 weeks following administration of the vaccine.

- E 19. Participant who has received leukotriene antagonists/modifiers within 4 weeks before Visit 1, unless participant is on a continuous treatment for at least 30 days
- E 20. Participant who has initiated allergen immunotherapy within 3 months before Visit 1 or has planned to begin therapy or change its dose during the screening or intervention period
- E 21. Participant who receives concomitant treatment prohibited in the study (see [Section 6.8](#))
- E 22. Participant who has received either intravenous immunoglobulin therapy and/or plasmapheresis within 30 days before Visit 1

Diagnostic assessments

- E 23. Participants with any of the following results at Visit 1:
 - a) Positive (or indeterminate) hepatitis B surface antigen (HBsAg), or
 - b) Positive total hepatitis B core antibody (HBcAb) and a negative HBsAg with positive hepatitis B virus (HBV) DNA, or
 - c) Positive hepatitis C virus (HCV) antibody with positive HCV RNA.

Noncompliance with diary completion

- E 24. Participants who do not demonstrate the following for acceptable compliance: completing the diary for any 4 mornings in the 7 days immediately preceding the Baseline Visit (Visit 2)

Other exclusions

- E 25. Individuals accommodated in an institution because of regulatory or legal order; prisoners or participants who are legally institutionalized
- E 26. Participant not suitable for participation, whatever the reason, as judged by the Investigator, including medical or clinical conditions or participants potentially at risk of noncompliance with study procedures
- E 27. Participants who are employees of the clinical study site, other individuals directly involved in the conduct of the study, or immediate family members of such individuals (in

conjunction with Section 1.61 of International Council for Harmonisation - Good Clinical Practice [ICH-GCP] Ordinance E6)

- E 28. Any specific situation during study implementation/course that may lead to ethical concerns
- E 29. Participant who has sensitivity to any of the study interventions, or components thereof, or drug or other allergy that, in the opinion of the Investigator, contraindicates participation in the study

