- b If alkaline phosphatase is elevated, consider fractionating.
- c In case of results showing HBsAg (negative), and HBcAb total or HBcAb IgM (positive), an HBV DNA testing will be performed and should be confirmed prior to enrollment. Participants who are HBcAb (positive) and HBV DNA (negative) at Visit 1 will require HBV DNA monitoring at Visits 6, 7, and 8 and at the participant's last visit (refer to SoA [[Section 1.3](#)]).
- d In case of results showing HCV Ab (positive), HCV RNA testing will be performed and should be confirmed prior to enrollment.
- e An IGRA is required only for participants without history of active/latent TB.

Investigators must document their review of each laboratory safety report.

10.3 APPENDIX 3: AES AND SAES: DEFINITIONS AND PROCEDURES FOR RECORDING, EVALUATING, FOLLOW-UP, AND REPORTING

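### Schedule of Activities footnote i leaves HBV DNA and HCV RNA testing to the Investigator, while Appendix 2 requires both before enrollment

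*Protocol*

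**What the plan says.** Two places in the protocol govern the confirmatory test after positive hepatitis serology.

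- **Schedule of Activities (Section 1.3), footnote i.** For a participant who is HBsAg negative and HBcAb positive (total or IgM), "HBV DNA testing may be performed prior to enrollment to rule out a false positive". The condition is that the Investigator suspects a false positive or finds the serological status unclear. For a positive HCV antibody, "HCV RNA testing may be performed to rule out a false positive, if the Investigator believes the participant is a false positive". No timing is given for the HCV test.
- **Appendix 2 (Section 10.2), notes c and d.** For the same hepatitis B serology, "HBV DNA testing will be performed and should be confirmed prior to enrollment". For a positive HCV antibody, "HCV RNA testing will be performed and should be confirmed prior to enrollment". Neither note depends on the Investigator's opinion.

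Two other provisions use the results:

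- **Section 5.2, E 23.** Item (b) excludes "Positive total hepatitis B core antibody (HBcAb) and a negative HBsAg with positive hepatitis B virus (HBV) DNA". Item (c) excludes "Positive hepatitis C virus (HCV) antibody with positive HCV RNA".
- **Schedule of Activities, footnote j.** This sets the check during the study: "Participant who are HBcAb (positive) and HBV DNA (negative) at Visit 1 will require HBV DNA monitoring". The check is scheduled four times, from Visit 6 to the final visit. If a result turns positive, treatment is interrupted and the participant is referred to a hepatologist. Section 7.1.3 repeats this rule for participants who require the monitoring.

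**The concern.** The same serology leads to an optional test under one rule and a required test under the other. The test result decides eligibility under E 23(b) and (c). For hepatitis B it also decides whether a participant enters DNA monitoring during the study. If the test is skipped, neither decision can be made as intended.

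What is at stake is uniform eligibility across sites and, for hepatitis B, a planned safety check during treatment. For hepatitis C only the eligibility check is affected, because the protocol plans no HCV RNA monitoring. No efficacy estimate depends on this.

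**Working it through.** No formula applies. The check sets the texts side by side and follows what happens if a site acts on footnote i alone.

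| Item | Footnote i | Appendix 2, notes c and d |
|---|---|---|
| HBV DNA after HBsAg negative, HBcAb total or IgM positive | Optional, on Investigator belief | Required |
| HBV DNA timing | Before enrollment, if done | Before enrollment |
| HCV RNA after positive HCV antibody | Optional, on Investigator belief | Required |
| HCV RNA timing | Not stated | Before enrollment |

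**Step 1: is this current text?** Yes. The amendment history (Appendix 14) is marked not applicable, so neither wording is superseded.

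**Step 2: does another section settle the conflict?** Mostly, but not expressly. Section 8.2.4 takes the list of tests from Appendix 2 and their timing and frequency from the Schedule of Activities. Section 8 wants all screening evaluations completed and reviewed to confirm eligibility. Section 5.4 allows no waiver. These point to Appendix 2. But Section 8 also makes adherence to the Schedule of Activities a requirement, and no sentence says that Appendix 2 prevails over a footnote to that schedule. The Appendix 2 tests are run by local laboratories in a multicenter study, so the documents show no central process that would add the viral test automatically.

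**Step 3: what does E 23 do without a result?** Items (b) and (c) exclude on a positive DNA or RNA result. Neither says how a missing result counts. Read literally, an untested antibody-positive participant does not meet either exclusion.

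**Step 4: what does footnote j do without a result?** It needs two findings at Visit 1: HBcAb positive and HBV DNA negative. With no DNA result the second is absent and monitoring is not triggered. The checks lost are those at Visits 6, 7, 8 and 9, that is Weeks 16, 24, 40 and 52: four checks. The interruption rule in Section 7.1.3 is addressed to participants who require this monitoring, so an untested participant falls outside it too.

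**Step 5: what remains?** Routine laboratory assessments, including ALT, are scheduled after baseline at Weeks 8, 24 and 52. The ALT stopping rule (Section 7.1.2) applies to everyone. Appendix 2 lets the Investigator order additional tests at any time.

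**The case against.** The strongest reply is that the two rules do not collide in practice. One permits and the other requires, so a site that tests obeys both. Section 8.2.4 makes the tests defined in Appendix 2 obligatory, E 23(b) and (c) cannot be confirmed without the viral result, and Section 5.4 allows no waiver. For harm to follow, a site would have to overlook Appendix 2, enroll with an exclusion unassessed, and find no reason to exclude under E 01 (active hepatobiliary disease or raised ALT), E 15 or E 26.

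Much of this stands. It shows which rule was meant and makes omission less likely. It does not remove the problem: a site that reads the optional wording in a schedule it is told to follow has a textual basis for not testing.

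A second reply is that footnote i, whose stated purpose is to rule out a false positive, may treat a positive antibody as disqualifying unless the viral test clears it. Section 5.4, which bars rescreening after a positive hepatitis test, fits that reading. An untested participant would then be kept out, not let in. But E 23 would admit that person after a negative DNA or RNA result, so sites would still apply different eligibility rules.

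A reader might also infer that E 23(b) is too narrow, because it names total HBcAb while the testing trigger also covers IgM. The documents do not support a change there. The panel in footnote i lists total whenever IgM is run, total HBcAb would ordinarily be expected to include IgM, and nothing shows that an IgM-positive, total-negative result is a realistic case.

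**Conclusion.** The inconsistency is real. Footnote i permits a site to omit two tests that Appendix 2 requires, and E 23(b), E 23(c) and the hepatitis B monitoring rule rely on their results. For an untested HBcAb-positive participant, all four scheduled HBV DNA checks would lack a trigger. For HCV the effect is limited to E 23(c).

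The number of participants affected is unknown. About 25 are to be enrolled, and the documents give no rate of positive HBcAb or HCV antibody. Whether sites would actually skip the test cannot be judged either, because the laboratory manual is not among the documents. The consequence therefore rests on an assumption: that at least one site acts on footnote i and has an antibody-positive candidate.

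A reader might infer that infected participants will be enrolled or left without liver monitoring. The documents do not support that. Sections 5.4, 8 and 8.2.4 point to mandatory testing, and routine ALT and its stopping rule apply regardless. Sample size and the primary analysis are unaffected. This is a minor safety and eligibility consistency correction.

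**What to change.** In footnote i, remove the optional wording and the conditions on the Investigator's belief. Replace them with the Appendix 2 wording for both tests: for HBsAg-negative, HBcAb-positive (total or IgM) participants, "HBV DNA testing will be performed and should be confirmed prior to enrollment"; for HCV antibody-positive participants, "HCV RNA testing will be performed and should be confirmed prior to enrollment". This also supplies the missing timing for HCV RNA. Footnote j, E 23 and Section 7.1.3 can stay as they are, because their inputs will then always exist.

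The cost is low: one footnote changes, and no test is added beyond what Appendix 2 already requires. It is still a protocol amendment, so the approval steps in Section 10.1.1 apply where relevant. It could be carried with the next amendment, with a clarification to sites that the tests in notes c and d are mandatory.
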